### 4.2 Endpoints

### 4.2.1 Primary Endpoints

For the primary endpoints, plots of the mean values for section 1 questions Q1-3, and questions in section 2 for total DHEQ score – section 2 (sum Q1-34), each of the domain's mean values (Restrictions – sum Q1-4, Adaptation – sum Q5-16, Social Impact – sum Q17-21, Emotional Impact – sum Q22-29, Identity – sum Q30-34), Global oral health (Q35) and Effect of life overall (sum Q36-39) over 24 weeks to assess QoL over time.

### 4.2.2 Exploratory/Safety Endpoints

- Plot over time in DHEQ mean scores for each sub-group
- DHEQ Mean scores over time compared to baseline (0, 4, 8, 12, 16, 20 and 24 weeks) to be analysed for overall DH sufferers and each sub-group
- Percentage of DH sufferers who agree (score 5-7) to items in each respective domain at baseline and week 24
- Numeric Pain Rating Scale (NPRS) Mean scores over time compared to baseline (0, 4, 8, 12, 16, 20 and 24 weeks) to be analysed for overall DH sufferers and each sub-group
- Plot over time in NPRS mean scores (0, 4, 8, 12, 16, 20 and 24 weeks) for overall DH sufferers and each sub-group
- Percentage of DH sufferers who achieve pain reduction identified as clinically important (pain reduction NPRS > 30%) for overall DH sufferers and each sub-group
- Satisfaction Numerical rating scale (NRS) for overall DH sufferers and each sub-group
- Summary of oral hygiene habits of DH sufferers according to oral hygiene questionnaire

## 4.3 Analysis

### 4.3.1 Population to be Analyzed

The Screened population will include subjects who sign the eIC and enter the screening process of assessment of inclusion and exclusion criteria.

The Enrolled population will include all subjects who meet the inclusion/exclusion criteria and identified by the screening questionnaire

The Safety population will include all subjects who receive at least one dose of study product. Safety population will be used of safety variables.

PPD	GSK-001 SAP	
ווט	Page 10 of 14	Version 1.0

The modified Intent-To-Treat (mITT) population will include all subjects who receive at least one dose of study product and have at least one post baseline DHEQ-48 questionnaire data. Efficacy data will be summarized using the mITT population only.

### 4.3.2 Sub-group Classification

A total of 4 different groups will be identified at screening for the purposes of sub-group analyses:

- Age group
  - ≤ 40 years old
  - > 40 years old
- Diagnosis
  - self-reported DH without previous diagnosis by a dentist
  - self-reported DH with previous diagnosis by a dentist
- Use of sensitivity toothpaste
  - Non-users will include subjects who are not currently using a sensitivity toothpaste e.g., first-time user
  - Intermittent users will include subjects who sometimes use a sensitivity toothpaste
  - current users will include subjects who regularly (daily) use a sensitivity toothpaste
- Self-reported DH frequency
  - frequent = Several times a day, Once a day, Several times a week
  - less frequent = Once a week, Several times a month, once a month, less than once a month

### 4.3.3 Demographics

Age and other continuous demographic and baseline variables will be summarized using descriptive statistics such as mean, range, median and standard deviation. Gender, race, ethnicity and other categorical demographic and baseline variables will be summarized using frequency counts and percentages for the safety and mITT populations.

PPD	GSK-001 SAP	
1 1 D	Page 11 of 14	Version
	11 of 14	1.0

### 4.3.4 Compliance

Study product compliance and compliance to the study schedule will be tabulated and summarized for the safety population.

Summaries will include a simple yes/no frequency (and percent) count at each timepoint:

- Summary of completion to study schedule and assessments (yes/no)
- Summary of product usage according to product instructions (yes/no)
- Summary of number of tubes remaining at the end of the study (number remaining) into three categories: 2 or less tubes, 3 to 6 tubes, and more than 6 tubes.

A listing of number of tubes remaining per subject will also be produced.

#### 4.3.5 Prior and Concomitant Medications

Concomitant medications taken during the study will be listed for the safety population.

### 4.3.6 Primary Objective Analysis

For the primary objective, plots of the mean values for section 1 questions Q1-3, and questions in section 2 for total DHEQ score – section 2 (sum Q1-34), each of the domain's mean values (Restrictions – sum Q1-4, Adaptation – sum Q5-16, Social Impact – sum Q17-21, Emotional Impact – sum Q22-29, Identity – sum Q30-34), Global oral health (Q35) and Effect of life overall (sum Q36-39) will be presented over 24 weeks to assess QoL over time in the overall population of DH sufferers, graphically.

#### 4.3.7 Exploratory/Safety Objectives Analysis

#### 4.3.7.1 Safety of the Study Product

All AEs will be coded using MedDRA. AEs will be categorized as oral and non-oral by PPD prior to database lock. The number of AEs/SAEs and number of subjects with AEs/SAEs will be listed and tabulated.

Adverse events will be listed individually with indicators as to the event's description, start and end time, severity, and relatedness to product.

### 4.3.7.2 Exploratory Objective 2

Plot over time in DHEQ mean scores for each sub-group

For the exploratory objective relating to sub-groups, plots of the mean values for section 1 questions Q1-3, and questions for section 2 total DHEQ score - section 2 (sum Q1-34), each of the domain's mean values (Restrictions - sum Q1-4, Adaptation - sum Q5-16, Social Impact -

PPD	GSK-001 SAP	
	Page 12 of 14	Version 1.0
	12 01 14	1.0

sum Q17-21, Emotional Impact – sum Q22-29, Identity – sum Q30-34), Global oral health (Q35) and Effect of life overall (sum Q36-39) will be presented over 24 weeks to assess QoL over time in the further characterisation of DH sufferers by sub-group classification, graphically.

## 4.3.7.3 Exploratory Objective 3

DHEQ Mean scores over time compared to baseline (0, 4, 8, 12, 16, 20 and 24 weeks) to be analysed for overall DH sufferers and each sub-group

The exploratory response variable is the DHEQ mean scores at 0, 4, 8, 12, 16, 20 and 24 weeks respectively in total score, each of the DHEQ domain scores, questions Q1-3, Global oral health, and Effect of life overall.

An Analysis of Variance (ANOVA) model will be used to analyze the DHEQ score as the response variable and timepoint as the dependent variable. Subject will be included as a random effect. Each post baseline timepoint will be compared to baseline using the adjusted means from the time variable from the model.

For the analysis of the 4 subgroups, an extra factor for the subgroup will be included along with the subgroup\*timepoint interaction. This will enable to look at the differences between sub-group and the interaction term will enable adjusted means of each subgroup over time.

For the ANOVA if the underlying assumptions are not met, alternative methods will be sought, including transformations or non-parametric methods.

Each of the DHEQ items were summarized by time point (Baseline, Week 4, 8, 12, 16, 20 and 24).

### 4.3.7.4 Exploratory Objective 4

Percentage of DH sufferers who agree (score 5-7) to items in each respective domain at baseline and week 24

A table for percentage of consumers who agree (score 5-7) to items in each domain at baseline and at week 24 respectively will also be presented as part of this objective. Percentage will be presented per each question.

## 4.3.7.5 Exploratory Objective 5

Numeric Pain Rating Scale (NPRS) Mean scores over time compared to baseline (0, 4, 8, 12, 16, 20 and 24 weeks) to be analysed for overall DH sufferers and each sub-group

The exploratory response variable is the NPRS mean score at 0, 4, 8, 12, 16, 20 and 24 weeks. An Analysis of Variance (ANOVA) model will be used to analyze the NPRS score as the response variable and timepoint as the dependent variable. Subject will be included as a

PPD	GSK-001 SAP	
1 1 0	Page 13 of 14	Version 1.0

random effect. Each post baseline timepoint will be compared to baseline using the adjusted means from the time variable from the model.

For the analysis of the 4 subgroups, an extra factor for the subgroup will be included along with the subgroup\*timepoint interaction. This will enable to look at the differences between sub-group and the interaction term will enable adjusted means of each subgroup over time.

For the ANOVA analyses if the underlying assumptions are not met, alternative methods will be sought, including transformations or non-parametric methods.

A plot of NPRS mean scores at each timepoint will also be presented along with a table reporting the percentage of participants who achieve pain reduction identified as clinically important (pain reduction NPRS > 30%).

#### 4.3.7.6 Exploratory Objective 6

Satisfaction Numerical rating scale (NRS)

The satisfaction Numerical rating scale will be summarized using frequencies at week 24. Similar summaries will be presented for overall population and each of the subgroups.

### 4.3.7.7 Exploratory Objective 7

Oral hygiene habits of DH sufferers according to oral hygiene questionnaire

A summary of oral hygiene habits at baseline will be provided as part of this objective

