12.4 Statistical Analyses

Additional details of the proposed statistical analysis will be documented in the statistical reporting and analysis plan (RAP), which will be written following finalization of the protocol and prior to study analysis (as appropriate). This section is a summary of the planned statistical analyses including primary and exploratory endpoints. Additional details for exploratory endpoints will be further described in detail in the RAP.

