### Scope

This document describes the analysis plan for the statistical analysis of the study GSK-001, study explanation.

This Statistical Analysis Plan (SAP) will provide details to further elaborate statistical methods as outlined in the study protocol and describe the analysis conventions to guide the statistical programming work.

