#### 4.3.8 Missing Values

The digital implementation of the PPD Application limits the possibility of missing values, as participants are unable to submit questionnaires if they are incomplete.

For the DHEQ data, for any timepoint if response is missing will be excluded from the primary analysis however the data available for each subject (even though some time points may be missing) will still be included in the analysis.

For secondary/exploratory analyses missing data will be imputed. Multiple imputation by fully conditional specification (FCS MI) will be utilized if the missing data meet the assumption of Missing At Random (MAR) or Missing Completely At Random (MCAR). Demographic data between subjects with missing and non-missing data will be compared to identify any statistically significant differences. If no differences, data will be assumed at least MAR.

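### The visit-versus-baseline ANOVA has only a random subject effect, so its standard errors are right only under sphericity, and the plan names no check or covariance remedy

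*SAP*

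**What the plan says.** SAP 4.3.7.3 models the DHEQ score at weeks 0, 4, 8, 12, 16, 20 and 24 on timepoint, with subject as a random effect. The text calls timepoint the dependent variable; I read it as the seven-level explanatory factor. The random term and the comparison are given as: "Subject will be included as a random effect. Each post baseline timepoint will be compared to baseline using the adjusted means" for timepoint. SAP 4.3.7.5 uses the same model for NPRS, and Protocol 12.4.3 has the same wording for both. Subgroup models add a subgroup factor and its interaction with timepoint. None of these sections names a residual covariance structure.

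The only safeguard is that "if the underlying assumptions are not met, alternative methods will be sought, including transformations or non-parametric methods".

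On missing data, SAP 4.3.8 states: "For secondary/exploratory analyses missing data will be imputed". The method is multiple imputation by fully conditional specification.

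Protocol 12.4 leaves the detail to the analysis plan: "Additional details for exploratory endpoints will be further described in detail in the RAP". The SAP's Scope section says that it "will provide details to further elaborate statistical methods as outlined in the study protocol". On this model the SAP repeats the protocol and adds nothing.

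**The concern.** A random subject effect with independent residuals forces equal variances and equal correlations across all seven visits. With complete data, each of the six baseline contrasts then gets the same standard error, built from the average of all 21 pairwise difference variances. If visits far apart correlate less than adjacent ones, the model overstates precision at late visits and understates it at week 4. The same overstatement arises, at every visit, if the pre-treatment baseline correlates less with the treated visits than they do with each other.

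Nothing in the documents supports equal correlation over 24 weeks, and SAP 4.1 says there is no prior information on DHEQ use in a real-world setting. The assumptions clause does not close the gap: it names no sphericity check or trigger, and neither of its examples models the covariance. Imputation does not close it either, because the same model is fitted to each completed data set.

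These contrasts are the stated analysis of the endpoint listed in SAP 4.2.2 as "DHEQ Mean scores over time compared to baseline (0, 4, 8, 12, 16, 20 and 24 weeks") and of its NPRS counterpart. They are the only model-based efficacy comparison in the plan.

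**Working it through.** **Inputs from the documents.** Seven visits; six contrasts with baseline; about 650 enrolled, 400 completers and 40% drop-out (SAP 4.1). The enrolment figure reproduces approximately: 400/(1 − 0.40) = 667 against 650, and 650 × 0.60 = 390 against 400, both within 3%. I use 390 at week 24.

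**Assumptions.** The documents give no correlations, variances or test level. The correlation patterns below, equal visit variances and a two-sided 5% level are mine.

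**Complete-data formula.** The model variance of a contrast is 2·MSE/n, and the expected value of 2·MSE is the mean of the 21 pairwise difference variances. The true variance is Var(visit k − baseline)/n. So

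- model SE / true SE = √(mean of the 21 difference variances / Var(visit k − baseline))
- type I error = 2·(1 − Φ(1.96 × ratio))

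**Worked case, correlation falling linearly from 0.75 (adjacent visits) to 0.50 (weeks 0 and 24).** The difference variance is 2(1 − ρ): 0.50, 0.60, 0.70, 0.80, 0.90, 1.00 for lags 1 to 6, with 6, 5, 4, 3, 2 and 1 pairs. The sum is 3.0 + 3.0 + 2.8 + 2.4 + 1.8 + 1.0 = 14.0, and the mean is 14.0/21 = 0.667. At week 24 the ratio is √(0.667/1.00) = 0.82 and the type I error 2·(1 − Φ(1.60)) = 11.0%. At week 4 the ratio is √(0.667/0.50) = 1.15.

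**Planned analysis.** This was simulated with 20,000 trials per pattern: 620 mITT subjects (assumed), monotone MCAR dropout in equal steps to 390 at week 24, 20 sequential-regression imputations, and Rubin's rules with Barnard-Rubin degrees of freedom.

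| Assumed pattern | Mean of 21 difference variances | Week 24 difference variance | Week 24 ratio and type I error, complete | Week 24 ratio and type I error, imputed |
|---|---|---|---|---|
| Equal correlation | same for all pairs | same | 1.00, 5.0% | 1.00, 4.8% |
| Decay 0.75 to 0.65 | 11.9/21 = 0.567 | 0.70 | 0.90, 7.8% | 0.93, 6.9% |
| Decay 0.75 to 0.50 | 14.0/21 = 0.667 | 1.00 | 0.82, 11.0% | 0.87, 8.7% |
| AR(1) 0.8 | 17.61/21 = 0.839 | 1.476 | 0.75, 14.0% | 0.81, 11.0% |
| Baseline–post 0.5, post–post 0.75 | (6 × 1.0 + 15 × 0.5)/21 = 0.643 | 1.00 | 0.80, 11.6% | 0.84, 10.0% |

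**By visit, imputed, decay 0.75 to 0.50 (weeks 4 to 24):** 1.15, 1.05, 0.99, 0.93, 0.89, 0.87. The SE is too large at weeks 4 and 8 and too small from week 16. The week 24 95% half-width is 0.079 SD as modelled against 0.090 SD true.

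**Sensitivity.**
- With an mITT of 500 or 650 in that pattern, the week 24 ratio is 0.85 (9.6%) or 0.87 (8.5%).
- Fitted to observed data without imputation, the week 24 ratios for the four unequal patterns, in table order, are 0.90, 0.81, 0.74 and 0.87.
- Unequal variances, complete data, correlation 0.65 throughout. Post-baseline SD 0.8 times baseline: √[((15 × 0.448 + 6 × 0.60)/21)/0.60] = 0.905 (7.6%). SD 1.2 times baseline: √[((15 × 1.008 + 6 × 0.88)/21)/0.88] = 1.05 (3.9%). The second errs on the cautious side.

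**Alternative model.** In the same simulations an unstructured covariance gave SE ratios of 0.99 to 1.02 and type I errors of 4.6% to 5.3% at all six visits, in every pattern and mITT size.

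**The case against.** - **Weight.** The primary objective is descriptive and is met by plots. The model serves exploratory objectives with no hypothesis, test level or formal sample size, so a type I error rate describes a test the plan never defines. In the central pattern the interval is off by about 0.01 SD on each side at week 24, and a change large enough to matter would be read the same way. This stands as a limit on importance. It does not make the standard errors right.
- **Unknown size.** The range includes no error and a cautious error, and the largest figure (14.0%) needs complete data, which this study will not have. This stands, so the imputed figures should carry the point.
- **The assumptions clause.** Sphericity is an underlying assumption of this ANOVA, and the clause is open-ended, so a covariance model is not excluded. A paired non-parametric comparison of each visit with baseline would also avoid sphericity. Both stand. What remains is that no check, trigger or particular method is named, so the published model is what would be run by default.
- **Reading.** A random subject effect does not strictly exclude a structured residual. True, but none is stated, and independent residuals are the natural reading.

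**Conclusion.** The concern holds. As written, the DHEQ and NPRS contrasts rest on sphericity, which the plan neither justifies nor checks. With the planned imputation, the week 24 SE is between 0.81 and 1.00 of its true value across the patterns tried, with type I error from 11.0% to 4.8%. Where correlation decays, the error reverses at early visits.

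This rests on assumed correlations, equal visit variances, an assumed two-sided 5% level, an mITT of 620 and MCAR dropout to 390. The effect is confined to the standard errors, and any intervals or p-values, of the exploratory DHEQ and NPRS contrasts, overall and by subgroup. The primary plots and the balanced-data mean changes do not move. It should be changed because the remedy is cheap, not because it threatens the primary objective.

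**What to change.** In SAP 4.3.7.3 and 4.3.7.5, replace the random-subject ANOVA with a REML repeated-measures model: fixed timepoint, plus subgroup and subgroup-by-timepoint where planned, and an unstructured within-subject covariance in place of the random subject effect. Fit it to each imputed data set and combine by Rubin's rules. If it does not converge, use a simpler structure with a robust (sandwich) variance. Align the model sentence in Protocol 12.4.3, since it names the random effect.

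The validating statistician has an easy check: in the overall model on a completed data set, each contrast SE equals SD(change)/√n.

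The cost is wording and slightly more programming. Seven visits give 7 × 8/2 = 28 covariance parameters, which 390 or more subjects support. Under decay from 0.75 to 0.50 the week 24 half-width as reported goes from 0.079 to 0.091 SD, and the week 4 half-width narrows from 0.064 to 0.056 SD. If correlation really is equal, almost nothing is lost: the week 24 half-width is 0.078 SD under both models, with type I errors of 4.8% (planned) and 4.9% (unstructured).

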Eligible subjects will complete the Dentine Hypersensitivity Experience Questionnaire (DHEQ), a validated, condition specific measure of impacts on everyday life for DH sufferers (Baker *et al*, 2014) (Boiko *et al*, 2010), at baseline and over 24-week period. This will the first study where the DHEQ will be used in a real-world setting, therefore the choice of the time points (0, 4, 8, 12, 16, 20 and 24 weeks) relates to published GSKCH data (Mason *et al*, 2019), which showed statistically significant changes from baseline at least after 8 weeks for DHEQ total score, at least after 12 weeks for the slowest domain (Identity) and at least after 24 weeks for global oral health.

In addition, to assess effectiveness, the use of NPRS scale will be used to evaluate the percentage of subjects who achieve pain reduction from the participant perspective (pain reduction NPRS > 30% has been identified as clinically important in previous pain studies (Hawker *et al*, 2011). Furthermore, subjects will be asked to rate their satisfaction with treatment after 24 weeks (Heft *et al*, 2018; van Berckel *et al*, 2017).

The rationale for a single arm design in a long-term DH study which evaluates the participant-reported OHrQoL outcomes was previously described by Mason and colleagues (Mason *et al*, 2019). A commercially available toothpaste will be used in this open label study; and the dosage regimen will allow the subjects to use the product as recommended for sensitivity relief according to commercial tube instructions, as per nature of the RWE study.

Clinical Protocol

Protocol Number: 216953

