12.4.4 Exclusion of Data from Analyses

Exclusion of any data from the analyses will be determined during a data review meeting prior to database lock and pre-defined in the RAP. Any reasons for exclusion from an analysis population will be listed, if applicable. As there is no PP analysis planned, only an assessment of subjects being in the safety and mITT populations will be made.

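### Does the exploratory >30% NPRS responder rate need a stated visit and a rule for a baseline score of 0?

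*SAP*

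**What the plan says.** The responder rate appears in the objectives tables of the protocol (1.1 and Table 3-1), in Protocol 4.2 and 12.4.3, and in SAP 4.2.2 and 4.3.7.5. Protocol 4.2 gives it some weight: "to assess effectiveness, the use of NPRS scale will be used to evaluate the percentage of subjects who achieve pain reduction". SAP 4.3.7.5 puts it in the same sentence as the plot of NPRS means by timepoint, and describes a table of "the percentage of participants who achieve pain reduction identified as clinically important (pain reduction NPRS > 30" (per cent). SAP 4.2.2 adds only that it is given overall and by sub-group.

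Neighbouring endpoints carry a visit. Item agreement is the "Percentage of DH sufferers who agree (score 5-7) to items in each respective domain at baseline and week 24", and for satisfaction, "The satisfaction Numerical rating scale will be summarized using frequencies at week 24".

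The protocol leaves detail to the analysis plan: "Additional details for exploratory endpoints will be further described in detail in the RAP" (12.4), and "Exclusion of any data from the analyses will be determined during a data review meeting prior to database lock and pre-defined in the RAP" (12.4.4). Two SAP rules bear on the denominator: "Efficacy data will be summarized using the mITT population only" (4.3.1) and "For secondary/exploratory analyses missing data will be imputed" (4.3.8).

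**The concern.** Two things appear to be left open.

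- **The visit.** The wording could be met by a reduction at week 24, by a rate at each visit, or by a reduction at any visit. All three can be computed, so nothing in the data would force the choice.
- **A baseline of 0.** The NPRS runs from 0 to 10 and asks about the last 24 hours (Protocol 9.3.1). Entry needs only self-reported sensitivity (Protocol 5.2), with no minimum score in the criteria, and the less frequent sub-group reaches down to symptoms less than once a month (SAP 4.3.2). Some subjects may therefore score 0 at baseline, where a percentage reduction is undefined. They might be dropped, kept as non-responders, or treated as missing and imputed.

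The rate is the one the protocol links to effectiveness and to clinical importance, and the study is open-label. If visit and denominator were truly free, they could be settled after the data had been seen, and the sub-group pattern could shift with the rule.

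**Working it through.** The documents state no responder rate, no share at baseline 0 and no power for this endpoint, so there is no planned figure to reproduce. The check is of the text, followed by conditional arithmetic.

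**1. Smallest qualifying drop.** Reduction = 100 × (baseline − visit) / baseline, and it must exceed 30.

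| Baseline | Smallest whole-point drop above 30% |
|---|---|
| 0 | none possible; ratio undefined |
| 1, 2, 3 | 1 point |
| 4, 5, 6 | 2 points |
| 7, 8, 9 | 3 points |
| 10 | 4 points |

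The equivalent condition, visit score below 0.7 × baseline, gives the same set. It also works at 0: a score below 0 cannot occur, so the subject is not a responder.

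**2. Which rule for zeros fits the text.**

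- *Drop them.* SAP 4.3.1 summarises efficacy in the mITT population, defined by at least one dose and at least one post-baseline DHEQ-48. It sets no NPRS condition. Protocol 12.4.4 ends by confining the assessment to membership of the safety and mITT populations. Removing zeros from one table would depart from both.
- *Impute them.* SAP 4.3.8 deals with missing values. An observed 0 is not missing.
- *Keep them as non-responders.* This needs no added rule: the subject is in mITT and has not achieved a reduction.

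The text therefore points to the third.

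**3. Size of the baseline-0 choice.** Let z be the share at 0 and r the rate among the rest. Dropping zeros gives r, keeping them gives r(1 − z), and the gap is r × z. Both inputs are assumed.

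| r | z | Dropped | Kept | Gap |
|---|---|---|---|---|
| any | 0 | r | r | 0 |
| 30% | 10% | 30% | 27% | 3 points |
| 50% | 20% | 50% | 40% | 10 points |
| 60% | 40% | 60% | 36% | 24 points |

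The largest gap needs two in five subjects to report no pain at baseline.

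**4. Size of the visit choice.** In a simulation with assumed inputs (baseline mean 4, SD 2.5, between-visit correlation 0.5, mean drop building to 1 point, zeros excluded), the rates at weeks 4 to 24 were 37.4%, 40.7%, 44.3%, 46.1%, 48.1% and 48.0%. Week 24 and a by-visit table cannot disagree about week 24, because the second includes the first; the by-visit table only adds the earlier values.

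The any-visit reading behaves differently: 86.3% in the same simulation, and 73.7% against about 31% at a single visit when the mean does not change at all. Large differences arise only under this reading. No passage speaks of a best response or of a response at any time, and a rate that reaches 74% with no mean change is not one a careful analyst would adopt unprompted.

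**The case for a change.** The strongest case for a change is that the plan set itself this task. The protocol promised further detail on exploratory endpoints and pre-defined exclusions, yet SAP 4.3.7.5 repeats the protocol sentence almost unaltered. In that sentence, the phrase about timepoints belongs to the plot and not to the table. A programmer who builds a percentage-change variable meets a division by zero and must do something about it. One line would settle both matters before the open-label data are examined, at almost no cost. The table shells mentioned in SAP 6.2 might do so, but they are not available here.

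Much of this stands. No visit is stated, the handling of 0 is not explicit, and an added line would do no harm.

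The step from there to a needed change does not stand. The denominator is not open in the way suggested, since SAP 4.3.1 with Protocol 12.4.4 already leads to the non-responder rule that an added line would state. The visit is open only between two readings that agree wherever they overlap. An added line would record the default and would not replace a stated method with a better one. The wider limitation, that a 24-hour rating catches chance quiet days at baseline or follow-up, remains under every rule.

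**Conclusion.** No change to the plan follows. The SAP omits a visit label and an explicit line on baseline 0 for one exploratory, descriptive percentage. No stated rule yields a wrong result, and the natural way to fill the gap is to tabulate the rate at week 24 or at each post-baseline visit, in the mITT population, with a baseline of 0 counted as no reduction. An analyst may note this in the table shells, and printing the number of subjects at baseline 0 would let a reader convert one rate to the other through the factor 1 − z. Both are optional.

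The sizes are conditional. The baseline-0 gap is r × z: zero if nobody scores 0, and 10 points at an assumed r of 50% and z of 20%. The visit gap is serious only under an any-visit reading that the documents do not suggest. The conclusion rests on reading the mITT rule as covering this table and on treating an observed 0 as data, not as missing. How missing follow-up scores enter the rate is a matter for SAP 4.3.8 and is not part of this point. The primary DHEQ analysis and the planned numbers are unaffected.
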